### Figure 1 Study Design

BED = bioequivalent dose; DoR = Duration of response; ECOG = Eastern Cooperative Oncology Group; Gy = gray; m = Month; mOS = median overall survival; mPFS = median progression-free survival; NSCLC = Non-small cell lung cancer; ORR = Overall response rate; OS12 = Overall survival at 12 months; PD = Progressive disease; PFS6, PFS12 = Progression-free survival at 6, 12 months, respectively; PRAE = Possibly related adverse event; PS = Performance status; q4w = Every 4 weeks; RT = radiation therapy

Approximately 102 patients will be treated with durvalumab in Europe and North America. Patients will be in complete response (CR), partial response (PR), or have stable disease (SD) following radiation therapy, as assessed by the Investigator and further supported by the screening imaging radiological assessment. Patients must not have progressed following radiation therapy, and radiation therapy must be completed within 6 weeks (42 days) prior to first durvalumab administration. The last dose of radiation therapy is defined as the day of the last radiation treatment session.

#### 1.2.1 Study Treatment

All patients will receive 1500 mg durvalumab via intravenous (IV) infusion q4w for up to a maximum of 12 months (up to 13 doses/cycles). The last administration of durvalumab will be on week 48 unless there is clinical progression, RECIST 1.1-defined radiological progression, unacceptable toxicity, withdrawal of consent, or another discontinuation criterion is met. If a patient's weight falls to 30 kg or below, the patient should receive weight-based dosing equivalent to 20 mg/kg of durvalumab q4w after consultation between Investigator and Study Physician, until the weight improves to > 30 kg, at which point the patient should start receiving the fixed dosing of durvalumab 1500 mg q4w.

The standard infusion time is 1 hour; however, if there are interruptions during infusion, the total allowed time should not exceed 8 hours at room temperature.

**Figure 2** **Durvalumab monotherapy dosing schedule**

		Durvalumab 1500 mg dose q4w				
Cycle		1	2	3	4	5 to 13 or PD a (max. 12 months)
Week		0-3	4-7	8-11	12-15	q4w ± 3 days until 48 weeks

max = Maximum; PD = Progression of disease; q4w = Every 4 weeks.

a Or until discontinuation of study drug due to any of the reasons

Patients may delay dosing under certain circumstances.

- Dosing may be delayed per the Dosing Modification and Toxicity Management Guidelines (see Section 8.4.5.1 of CSP), due to either immune-mediated adverse events (imAEs) or non-imAEs.
- If dosing must be delayed for reasons other than treatment-related toxicity, dosing will resume as soon as feasible.
- Dosing intervals of subsequent cycles may be shortened as clinically feasible in order to gradually align treatment cycles with the schedule of tumor efficacy (RECIST) and patient-reported outcomes (PRO) assessments. Subsequent time between 2 consecutive doses cannot be less than 22 days, based on the half-life of durvalumab (see the current Investigator's Brochure [IB] for durvalumab).

One cycle of treatment with durvalumab is equal to 28 calendar days.

The schedule of assessments including safety, tolerability, efficacy using RECIST version 1.1 and PROs based on questionnaires are detailed in the study assessment schedule in [Appendix A](#).

If imaging procedures were performed for alternate reasons prior to signing consent, these can be used for screening purposes with consent of the patient. However, all screening imaging results must have been obtained within 28 days prior to the first dose.

PRO and tumor efficacy (RECIST) assessment dates are not affected by dose delays and remain as originally scheduled, as they are based on the date of the first dose (not the date of therapy).

All other scheduled assessments must be performed relative to the start of the dosing cycle such that all laboratory procedures, etc, required for dosing should be performed within 3 calendar days prior to dosing.

### 1.2.2 Tumor Response Assessments

Tumor assessments using computed tomography (CT)/magnetic resonance imaging (MRI) will

be performed at the times specified in the schedule of assessment ([Appendix A](#)). RECIST 1.1 measurements as assessed by the Investigator will be used to derive the secondary variables of PFS, ORR, and DOR. The categorisation of objective tumor response assessment into complete response (CR), partial response (PR), stable disease (SD), progressive disease (PD) or not evaluable (NE) will be based on RECIST 1.1.

### **1.2.3 Overall Survival Assessments**

All patients in the study should be followed up for survival at months 2, 3, 4, 6, 8, 10, and 12 following treatment discontinuation or completion, and then every 12 weeks until death, withdrawal of consent, or the end of the study.

## **1.3 Number of Patients**

The primary objective of this study is to assess the safety and tolerability of durvalumab which is defined as Grade 3 and Grade 4 PRAEs observed within 6 months after the initiation of durvalumab treatment. In addition, safety and tolerability of durvalumab will be characterized for the cohorts of patients who received Standard Radiotherapy ( $60\text{ Gy} \pm 10\%$ ) or hypofractionated BED and patients who received palliative radiotherapy (40 to  $< 54\text{ Gy}$ ) or hypofractionated BED.

A total of approximately 102 patients are treated with durvalumab in 2 cohorts: approximately 59 patients in the Standard Radiotherapy Cohort and approximately 43 patients in the Palliative Radiotherapy Cohort. It is estimated that a sample size of a minimum 60 patients would be required to provide an adequate level of confidence in the estimated incidence of Grade 3 and 4 PRAEs occurring within 6 months after initiation of durvalumab treatment, which is the primary endpoint. With a sample size of 60 patients, the exact binomial 95% CI for an observed incidence rate of 12% would be 5% to 23%. If the underlying/true incidence rate was 12% as reported in PACIFIC (D4194C00006), on repeated implementations of this study, observing an incidence rate less than 5% or greater than 18.3% would be approximately 5% for each region/tail.

Furthermore, if there are 30 patients in each cohort (Standard Radiotherapy and Palliative Radiotherapy) and the true incidence of Grade 3 and Grade 4 PRAEs occurring within 6 months after initiation of durvalumab treatment is 12%, , the precision will be approximately  $\pm 13.0\%$  (95% CI: 3.1, 29.1) in each cohort.

An illustration of the precision around the varying incidence rate of Grade 3 and Grade 4 PRAEs for the patients overall and for each cohort (Standard Radiotherapy and Palliative Radiotherapy) is provided in Table 1.

**Table 1 Precision around varying incidence of Grade 3 and Grade 4 Possibly-Related Adverse Events**

Sample size	Grade 3 and Grade 4 PRAE Incidence Rate		
	10 %	12 %	15 %
60	3.8-20.5 ( $\pm$ 8.4)	5.0-23.0 ( $\pm$ 9.0)	7.1-26.6 ( $\pm$ 9.7)
30	2.1-26.5 ( $\pm$ 12.2)	3.1-29.1 ( $\pm$ 13.0)	4.7-32.7 ( $\pm$ 14.0)

PRAE = possibly related adverse event.

## 2. ANALYSIS SETS

### 2.1 Definition of Analysis Sets

With the exception of some summaries of patient disposition and particular individual patient data listings, which will be produced for all patients who provided informed consent and who were enrolled in the study, the Safety Analysis Set (SAF) will be used for listings, summaries, and analyses in the study.

#### 2.1.1 Safety Analysis Set

The Safety Analysis Set: will consist of all patients who received at least one dose (partial or in full) of durvalumab. The SAF will be used for analysis of all safety endpoints. In this safety study, the standard full analysis set will be same as SAF, therefore, the SAF will be used for analysis of efficacy endpoints as well.

For analysis of time-to-event endpoints, the SAF will be used with defined censored patients.

## 2.2 Protocol Deviations

### 2.2.1 Important Protocol Deviations

According to ICH E3 guidelines version dated 1995 ([ICH 1995](#)),

“Protocol deviations (PDs) consist of any change, divergence or departure from the study design or procedures defined in the protocol. Important protocol deviations (IPDs) are a subset of protocol deviations that may significantly affect the completeness, accuracy, and/or reliability of the study data or that may significantly affect a patient’s rights, safety or well-being.”

For this study, the following 4 general categories will be considered IPDs and will be summarized in the Clinical Study Report (CSR):

- Deviation 1: Patients who received treatment and who deviated from the following key entry criteria in Clinical Study Protocol (CSP):

- Inclusion Criterion 5: Histologically- or cytologically-documented NSCLC with locally-advanced, unresectable Stage III disease (according to the International Association for the Study of Lung Cancer [IASLC] Staging Manual Version 8 [IASLC 2016]).
  - (a) Imaging to rule out distant metastasis is required.
  - (b) Endobronchial ultrasound with biopsy is encouraged in patients with suspected lymph node involvement.
- Inclusion Criterion 6: Deemed ineligible for chemotherapy per Investigator assessment (eg, comorbidities, poor PS, etc).
- Inclusion Criterion 7: Receipt of radiation therapy that was completed within 42 days prior to first IP dose administration in the study.
- Inclusion Criteria 8: Patients must have received a total dose of radiation of 40 to 66 Gy (standard or hypofractionated BED). Note that patients will be assigned to Cohort A (standard radiation therapy [60 Gy  $\pm$  10% or hypofractionated BED]) or Cohort B (palliative radiation therapy [40 to < 54 Gy or hypofractionated BED]) based upon total dose of radiation received. Sites are encouraged to adhere to mean organ radiation dosing as follows:
  - a) Mean lung dose < 20 Gy and/or V20 < 35%;
  - b) Mean esophagus dose < 34 Gy;
  - c) Heart V45 < 35% or V30 < 30%. Heart V45 < 35% or V30 < 30%.
  - d) Note: Sites should be aware of the recent RTOG 0617 Study data (Bradley et al 2015) demonstrating that doses higher than 60 Gy may be associated with greater toxicity and worse efficacy. Patients with WHO/ECOG PS 2 or chronic lung disease (pulmonary emphysema or chronic obstructive pulmonary disease) must have received a V20 < 25%.
- Inclusion Criterion 9: Patients must not have progressed following radiation therapy, as per Investigator assessed RECIST 1.1 criteria.
  - (a) Patients with measurable disease and/or nonmeasurable and/or no evidence of disease assessed at baseline by computed tomography (CT)/magnetic resonance imaging (MRI) will be eligible for this study.
  - (b) Prior irradiated lesions may be considered measurable and selected as target lesions (TLs) providing they fulfil the other criteria for measurability.
- Inclusion Criterion 10: WHO/ECOG PS  $\leq$  2.
- Inclusion Criterion 11: No prior exposure to immune-mediated therapy including, but not limited to, anti-CTLA-4, anti-PD-1, anti-PD-L1, and antiprogrammed cell death ligand 2 (anti-PD-L2) antibodies, excluding therapeutic anticancer vaccines.
- Exclusion Criterion 1: Patients with locally-advanced NSCLC whose disease has progressed following radiation therapy.
- Exclusion Criterion 2: Mixed small-cell lung cancer and NSCLC histology.

- Exclusion Criterion 5: Uncontrolled intercurrent illness, including but not limited to, ongoing or active infection, symptomatic congestive heart failure, uncontrolled hypertension, unstable angina pectoris, uncontrolled cardiac arrhythmia, active interstitial lung disease (ILD), serious chronic gastrointestinal conditions associated with diarrhea, or psychiatric illness/social situations that would limit compliance with study requirement, substantially increase risk of incurring AEs or compromise the ability of the patient to give written informed consent.
- Exclusion Criterion 9: Active infection including tuberculosis (clinical evaluation that includes clinical history, physical examination and radiographic findings, and tuberculosis testing in line with local practice), hepatitis B (known positive hepatitis B virus surface antigen (HBsAg) result), hepatitis C, or human immunodeficiency virus (human immunodeficiency virus [HIV]; positive HIV 1/2 antibodies). Patients with a past or resolved hepatitis B virus infection (defined as the presence of hepatitis B core antibody [anti-HBc] and absence of HBsAg) are eligible. Patients positive for hepatitis C antibody are eligible only if polymerase chain reaction is negative for hepatitis C virus ribonucleic acid.
- Exclusion Criterion 14: Current or prior use of immunosuppressive medication within 14 days before the first dose of durvalumab. The following are exceptions to this criterion:
  - Intranasal, inhaled, topical steroids, or local steroid injections (eg, intra articular injection)
  - Systemic corticosteroids at physiologic doses not to exceed 10 mg/day of prednisone or its equivalent
  - Steroids as premedication for hypersensitivity reactions (eg, CT scan premedication)
- Deviation 2: The patient met discontinuation criteria but did not discontinue durvalumab (eg, patient withdrew consent, patient became pregnant).
- Deviation 3: The patient received a prohibited concomitant medication or procedure as detailed in Section 6.4 of the CSP or any other concomitant medication or procedure which, upon physician review of all medications and procedures prior to database lock (DBL), is considered to have a potential effect on study outcomes.
- Deviation 4: Missed visits, assessments, or treatments that, in the opinion of the principal investigator,
  - were due to the 2020 COVID-19 global pandemic and
  - there was a significant effect on either completeness, accuracy, and/or reliability of the patient's data, or the patient's rights, safety or well-being.

## 2.2.2 Monitoring of Protocol Deviations

Programmable PDs will be detected from the data recorded in the clinical database and will be reviewed at regular PD review meetings. At this meeting, the programmatically-derived PDs will be checked to ensure that they have been correctly classified as major or minor PDs.

On an ongoing basis throughout the study, monitoring notes or summaries will also be reviewed to determine any important post-entry deviations that are not identifiable via programming.

If the number of deviations which are considered to have the potential to impact the primary analysis is considered important, sensitivity analyses may be performed on subgroups. This will be decided during the data review meeting and before the DBL.

The final classification of IPDs will be made prior to DBL or data cut-off for final analysis. Any other deviations from monitoring notes or reports will be reported in an appendix to the CSR.

### **3. ANALYSIS VARIABLES**

#### **3.1 Derivation of RECIST Visit Responses**

For all patients, the RECIST tumor response data will be used to determine each patient's visit response according to RECIST version 1.1. It will also be used to determine, if and when a patient's disease has progressed in accordance with RECIST and their best objective response to study treatment.

The baseline radiological tumor assessment is part of the screening procedure and should be performed within 28 days after the end of radiotherapy, no more than 28 days before the start of durvalumab treatment, and ideally as close as possible to the start of study treatment. Tumor assessments will begin at 8 weeks  $\pm$  1 week after durvalumab initiation and continue every 8 weeks  $\pm$  1 week through 48 weeks (relative to the date of first dose of durvalumab), and then every 12 weeks  $\pm$  1 week thereafter until RECIST 1.1-defined PD, plus an additional regularly scheduled follow-up scan. The on-study schedule of q8w  $\pm$  1 week (following the first assessment at 8 weeks  $\pm$  1w after the first dose) for first 48 weeks and then q12w  $\pm$  1 w thereafter MUST be followed regardless of any delays in dosing. Additional scans can be completed per standard practice post disease progression.

From the investigator's review of the imaging scans, the RECIST tumor response data will be used to determine each patient's visit response according to RECIST version 1.1. At each visit, patients will be programmatically assigned a RECIST 1.1 visit response of CR, PR, SD or PD, using the information from target lesions (TLs), non-target lesions (NTLs) and new lesions and depending on the status of their disease compared with baseline and previous assessments. If a patient has had a tumor assessment which cannot be evaluated, then the patient will be assigned a visit response of not evaluable (NE) (unless there is evidence of progression in which case the response will be assigned as PD).

RECIST outcomes (ie, PFS and ORR etc.) will be calculated programmatically from site investigator data from overall visit responses.

### **3.1.1 Site Investigator Assessments Using RECIST 1.1**

#### **3.1.1.1 Target Lesions**

Measurable disease is defined as having at least one measurable lesion, not previously irradiated, which is  $\geq 10$  mm in the longest diameter (LD), (except lymph nodes which must have short axis  $\geq 15$  mm) with CT or MRI and which is suitable for accurate repeated measurements.

A maximum of five measurable lesions (with a maximum of two lesions per organ), representative of all lesions involved and suitable for accurate repeated measurement, should be identified as TLs at baseline. It may be the case that, on occasion, the largest lesion does not lend itself to reproducible measurement. In which circumstance the next largest lesion, which can be measured reproducibly, should be selected. If more than one baseline scan is recorded, then measurements from the one that is closest and prior to initiation of durvalumab will be used to define the baseline sum of TLs.

All other measurable lesions not recorded as TL, and all non-measurable lesions (or sites of disease) should be identified as non-target lesions (NTLs) at baseline. Measurements are not required for these lesions, but their status should be followed at subsequent visits.

For patients who do not have measurable disease at entry (ie, no TLs) but have non-measurable disease, evaluation of overall visit responses will be based on the overall NTL assessment and the absence/presence of new lesions (see Section [3.1.1.3](#) for further details). If a patient does not have measurable disease at baseline, then the TL visit response will be not applicable (NA).

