#### 1.1.2 Secondary Objectives

Secondary Efficacy Objectives	Endpoints / Variables
To assess the efficacy of durvalumab treatment in terms of progression-free survival (PFS) and overall survival (OS)	Median PFS according to Response Evaluation Criteria in Solid Tumors version 1.1 (RECIST 1.1) as assessed by the Investigator PFS6 and PFS12 according to RECIST 1.1 as assessed by the Investigator Median OS and OS12
To further assess the efficacy of durvalumab treatment in terms of objective response rate (ORR) and duration of response (DoR)	Objective response (OR) according to RECIST 1.1 as assessed by the Investigator DoR according to RECIST 1.1 as assessed by the Investigator
To assess the efficacy of durvalumab treatment in terms of lung cancer mortality	Lung cancer mortality

Secondary Safety Objectives	Endpoints / Variables
To further assess the safety and tolerability profile of durvalumab treatment, including all adverse events (AEs)	AEs, serious adverse events (SAEs), adverse events of special interest (AESIs), immune-mediated adverse events (imAEs), physical examinations, vital signs including blood pressure (BP) and pulse rate, electrocardiograms (ECGs) and laboratory findings including clinical chemistry, haematology and urinalysis

Note: Analysis of OR and DoR will be based upon Investigator assessment according to RECIST 1.1. Prior irradiated lesions may be considered measurable and selected as target lesions provided they fulfil the other criteria for measurability.

[figure not shown]
An AESI is an AE of scientific and medical interest specific to the understanding of durvalumab. AESIs for durvalumab include, but are not limited to, events with a potential inflammatory or immune-mediated mechanism and which may require more frequent monitoring and/or interventions such as steroids, immunosuppressants and/or hormone replacement therapy.

An imAE is defined as an AESI that is associated with drug exposure and is consistent with an immune-mediated mechanism of action and where there is no clear alternate etiology.

[figure not shown]

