**Table 2 Target Lesion Visit Responses**

Visit Responses	Description
Complete response (CR)	Disappearance of all TLs since baseline. Any pathological lymph nodes selected as TLs must have a reduction in short axis to <10 mm.
Partial response (PR)	At least a 30% decrease in the sum of the diameters of TL, taking as reference the baseline sum of diameters as long as criteria for PD are not met.
Stable disease (SD)	Neither sufficient shrinkage to qualify for PR nor sufficient increase to qualify for PD
Progression of disease (PD)	A $\geq 20\%$ increase in the sum of diameters of TLs and an absolute increase of $\geq 5\text{mm}$ , taking as reference the smallest sum of diameters since treatment started including the baseline sum of diameters.
Not evaluable (NE)	Only relevant in certain situations (ie, if any of the TLs were not assessed or not evaluable or had a lesion intervention at this visit; and scaling up could not be performed for lesions with interventions). Note: If the sum of diameters meets the progressive disease criteria, progressive disease overrides not evaluable as a TL response.
Not applicable (NA)	No TLs are recorded at baseline.

CR: Complete response; NA: Not applicable; NE: Not evaluable; PD: Progressive disease; PR: Partial response; SD: Stable Disease; TL: target lesion

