**Table 3 NTL Visit Responses**

Visit Responses	Description
Complete response (CR)	Disappearance of all NTLs since baseline. All lymph nodes must be non-pathological in size (<10 mm short axis).
Non CR/non PD	Persistence of one or more NTLs with no evidence of progression.
Progression (PD)	Unequivocal progression of existing NTLs. Unequivocal progression may be due to an important progression in one lesion only or in several lesions. In all cases the progression MUST be clinically significant for the physician to consider changing (or stopping) therapy.
Not evaluable (NE)	Only relevant when one or some of the NTLs were not assessed and, in the Investigator's opinion, they are not able to provide an evaluable overall NTL assessment at this visit.  Note: for patients without TLs at baseline, this is relevant if any of the NTLs were not assessed at this visit and the progression criteria have not been met.
Not applicable (NA)	Only relevant if there are no NTLs at baseline.

CR: Complete response; NA: Not applicable; NE: Not evaluable; NTL non-target lesion; PD: Progressive disease; PR: Partial response; SD: Stable Disease; TL: target lesion

To achieve 'unequivocal progression' based on NTLs, there must be an overall level of substantial worsening in non-target disease such that, even in the presence of SD or PR in TLs, the overall tumor burden has increased sufficiently to merit a discontinuation of therapy. A modest 'increase' in the size of one or more NTLs is usually not sufficient to qualify for unequivocal progression status.

Details of any new lesions will also be recorded with the date of assessment. The presence of one or more new lesions is assessed as progression.

A lesion identified at a follow up assessment in an anatomical location that was not scanned at baseline is considered a new lesion and will indicate disease progression.

The finding of a new lesion should be unequivocal: ie, not attributable to differences in scanning technique, change in imaging modality or findings thought to represent something other than tumor.

New lesions will be identified via a Yes/No tick box. The absence and presence of new lesions at each visit should be listed alongside the TL and NTL visit responses.

A new lesion indicates progression, so the overall visit response will be PD irrespective of the TL and NTL response.

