**Table 4 Overall Visit Responses**

Target	Non-target	New Lesions	Overall Visit Response
CR	CR (or NA)	No (or NE)	CR
CR	Non-CR/Non-PD or NE	No (or NE)	PR
PR	Non-PD or NE or NA	No (or NE)	PR
SD	Non-PD or NE or NA	No (or NE)	SD
PD	Any	Any	PD
Any	PD	Any	PD
Any	Any	Yes	PD
NE	Non-PD or NE or NA	No (or NE)	NE
NA	CR	No (or NE)	CR
NA	Non-CR/Non-PD	No (or NE)	SD
NA	NE	No (or NE)	NE
NA	NA	No (or NE)	NED

CR complete response; PR partial response; SD stable disease; PD progression of disease; NE not evaluable; NA not applicable (only relevant if there were neither target nor non-target lesions at baseline); NED no evidence of disease.

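### SAP 3.1.1.1 excludes previously irradiated lesions from measurable disease, against the rest of the plan, and patients with no evidence of disease have no best-response category

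*SAP*

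**What the plan says.** **Irradiated lesions.** SAP 3.1.1.1 opens with "Measurable disease is defined as having at least one measurable lesion, not previously irradiated", followed by the usual size thresholds. The same section then makes the target-lesion (TL) visit response not applicable (NA) for a patient without measurable disease at baseline.

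Other places in the SAP say otherwise. The note under the objectives in 1.1.2 reads "Prior irradiated lesions may be considered measurable and selected as target lesions provided they fulfil the other criteria for measurability". Section 2.2.1, restating inclusion criterion 9(b), reads "Prior irradiated lesions may be considered measurable and selected as target lesions (TLs) providing they fulfil the other criteria for measurability". The subsection of 3.1.1.1 on irradiated lesions and lesion interventions also permits an irradiated TL, on condition that it is reproducibly measurable and no other lesion is available.

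The protocol grants the same permission in inclusion criterion 9(b) without the no-other-lesion condition, and in Appendix F with it. The Appendix F definition of a measurable lesion does not mention irradiation. Inclusion criterion 7 requires completed radiotherapy within 42 days before the first dose.

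**No evidence of disease.** Inclusion criterion 9(a) admits patients with no evidence of disease at baseline. SAP Table 4 gives them an overall visit response of NED when the TL and non-target-lesion (NTL) responses are both NA and there is no new lesion. SAP 3.1 lists CR, PR, SD and PD, plus NE, as visit responses. SAP 3.3.4 and 4.4.3 list CR, PR, SD, PD and NE for best objective response. None of these lists includes NED, and no mapping from NED to a listed category is given.

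**The concern.** The definition and the permissions cannot both hold. Sections 1.1.2 and 2.2.1 say that irradiated lesions may count as measurable, so they contradict the definition itself and do not merely carve out an exception to it. The visible part of SAP section 6 declares no departure from the protocol on this point. Because prior radiotherapy is an entry requirement, the clause could bear on the lesions most likely to be followed.

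SAP 3.1 derives response and progression outcomes programmatically from the overall visit responses. Two programmers following different sentences could therefore score the same patient differently. The objective response rate (ORR), best response and duration of response would be affected, and possibly progression-free survival (PFS).

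The NED gap is separate. A patient can have a visit response that the best-response table has no row for, while remaining in the Safety Analysis Set (SAF) denominator for ORR.

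**Working it through.** The plan states no figure on this point, so the check sets the rules side by side. The numerical examples only illustrate.

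**1. Outputs of SAP Table 4.** Its 12 rows produce six overall responses: CR, PR, SD, PD, NE and NED. The lists in 3.1, 3.3.4 and 4.4.3 hold five: CR, PR, SD, PD and NE. The one difference is NED.

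**2. Outputs when the TL response is NA.** The applicable rows are:
- NTL response CR gives CR.
- NTL response non-CR/non-PD gives SD.
- NTL response NE gives NE.
- NTL response NA gives NED.
- NTL progression or a new lesion gives PD.

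PR does not appear. A patient whose TL response is NA can respond only by complete response.

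**3. One irradiated lesion under each rule** (invented sizes).

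| Change | Scored as TL, SAP Table 2 | Literal 3.1.1.1, followed as NTL |
|---|---|---|
| 40 to 26 mm | 1 − 26/40 = 35% decrease, at least 30%: PR | Lesion persists: SD |
| 40 to 50 mm | 50/40 − 1 = 25% increase and +10 mm, at least 20% and 5 mm: PD | PD if the investigator judges the progression unequivocal |

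The NTL column follows from 3.1.1.1, which sends non-measurable lesions to the NTL list. The partial response is lost outright. Progression is still captured, but by investigator judgement instead of a measured threshold, so its date could differ. That is the only route by which PFS might change.

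**4. The permissions differ among themselves.** Protocol inclusion criterion 9(b), SAP 1.1.2 and SAP 2.2.1 have no no-other-lesion condition. Protocol Appendix F and the later subsection of SAP 3.1.1.1 do. A patient with two irradiated measurable lesions and no others is treated differently under the two sets.

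**5. NED and the denominators.** The NED share is not in the documents. Assume 10 of 102 treated patients, and borrow the 28.4% response rate that protocol 2.3.1 reports for PACIFIC for the remaining 92: 0.284 × 92 = 26.1, so 26 responders.
- SAF ORR: 26/102 = 25.5%, exact 95% CI 17.4 to 35.1, width 17.7 points.
- Patients with any baseline lesion: 26/92 = 28.3%, exact 95% CI 19.4 to 38.6, width 19.2 points.

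If best response were left blank for the NED patients, the default in SAP 4.1.1 (non-missing data as denominator) would put 28.3% in the best-response table beside an ORR of 25.5%, with 26 responders in both.

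**The case against.** The strongest reply is that the SAP already shows what it means. Section 3.1.1.1 introduces the relevant group with "For patients who do not have measurable disease at entry (ie, no TLs) but have non-measurable disease", and Table 2 defines NA as "No TLs are recorded at baseline". Nothing tells a programmer to discard a recorded TL because it was irradiated. Sites select TLs under the protocol, whose definition of measurability has no such exclusion. This stands as evidence that the phrase is stray and that the sensible derivation is the likely one. It does not remove the contradiction, because the SAP still states both rules.

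Three stronger readings are tempting, and the documents do not support them.

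- A reader might infer that a measured TL could shrink or grow and be scored NED, so that progression is missed. That requires the lesion to be recorded as a TL, have its measurements ignored, and also not be followed as an NTL. Section 3.1.1.1 says non-measurable lesions become NTLs. The Table 4 footnote calls NA "only relevant if there were neither target nor non-target lesions at baseline", which also argues against NED for a patient who has a lesion.
- A reader might infer that NED patients wrongly dilute ORR. Keeping them in the denominator is pre-specified: protocol 9.3 puts all analyses on the safety analysis set, and SAP 3.3.3 and 4.4.3 say the same for ORR. The lower percentage is a property of the chosen population.
- A reader might infer that the response tables will disagree. That needs NED patients to exist, their best response to be left blank, and the default denominator to be applied without the footnoted alternative that 4.1.1 allows. It is possible but not established.

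NED also does not break PFS. SAP 3.3.1 excludes only NE and missing visits from evaluable assessments, and a new lesion still gives PD.

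**Conclusion.** Two wording defects stand. First, SAP 3.1.1.1 states a rule on irradiated lesions that conflicts with other SAP sections and with the protocol. Applied literally, it removes partial response for patients whose only measurable lesions were irradiated. Second, NED is assigned in Table 4 but has no place in the visit-response list or the best-response categories.

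The reach is limited to descriptive secondary outputs: ORR, best response, duration of response and possibly PFS. The primary safety endpoint and the sample size are untouched. The size cannot be stated, because the documents give neither the number of patients whose only measurable lesions were irradiated nor the number with no lesion at baseline. The 10 of 102 used above is an assumption, and the 28.4% comes from a chemoradiotherapy trial. Since other SAP text points to the sensible derivation, the first defect is a risk of inconsistent programming; it does not show that the results will be wrong.

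**What to change.** - In SAP 3.1.1.1, delete the clause on prior irradiation. State that TL response is derived from the TLs the site recorded, with NA only when none were recorded, as in Table 2.
- Choose one condition for irradiated TLs and use it throughout. Protocol Appendix F and the later SAP 3.1.1.1 subsection require that no other lesion be available; protocol criterion 9(b) and SAP 1.1.2 and 2.2.1 do not. Since part of this text sits in the protocol, a short protocol clarification may be needed. Deriving response from the recorded TLs works under either wording.
- Add NED to the categories in SAP 3.1, 3.3.4 and 4.4.3, and use the SAF as denominator for best-response percentages. Align the Table 4 footnote on NA with the rows where only one of the two lesion types is absent.
- Keep SAF ORR as the main analysis. Optionally add a supportive ORR in patients with any TL or NTL at baseline, with the NED count shown.

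The cost is wording and, at most, one extra table; no new data are needed. The supportive interval would be slightly wider: 19.2 against 17.7 points under the assumed 10 NED patients of 102.
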